5.1 Subject Inclusion Criteria

- Pathological or clinical/radiological diagnosis of a neoplasm, either primary (e.g., malignant glioma) or secondary (metastasis from systemic malignancy) with a history of brain radiation therapy
- Completed fractionated radiation therapy (to 60 Gy for high grade gliomas) or stereotactic radiosurgery or hypofractionated radiation therapy (e.g. for brain metastases, anaplastic meningiomas), without or with concurrent chemotherapy
- New or increased enhancing brain lesion(s) OR nonenhancing brain lesion(s) if receiving anti-angiogenic therapy, which is considered indeterminate for tumor progression vs. radiation injury by the neuroradiologist or clinician
- Patient and/or guardian is able to provide written informed consent prior to study registration
- Age ≥18 years old

5.2 Subject Exclusion Criteria

- Claustrophobia
- Known allergic reaction to Gd-DTPA
- Any contraindication to gadolinium intravenous contrast as per standard Department of Radiology contrast guidelines
- Any contraindication to MRI (e.g., pacemaker, aneurysm clip, tissue expander).
- Pregnant or nursing female
- Unable to cooperate for MRI and/or PET/CT

6.0 RECRUITMENT PLAN

Patients for this study will be referred by members from the Departments of Radiation Oncology and Neurology. Patients will typically have a CT or MRI scan showing an increasing indeterminate lesion. All adult patients ≥18 years are eligible for participation regardless of sex or race. Every effort will be made to encourage eligible women and minorities to enroll in this study. Prior to study entry, the study staff will explain to each potential subject the research objectives, risks and benefits of study participation, alternative treatments available, and the subjects' rights and responsibilities. If the patient agrees to participate in the study, informed consent will be obtained by a consenting individual on the study. All patients must sign written informed consent prior to being registered on this protocol.

7.0 ASSESSMENT/EVALUATION PLAN

7.1 Imaging evaluation

The maximal abnormalities on the MRI perfusion scans and PET/CT scans will be recorded according to standard ROI and volume of interest (VOI) measurements:

FDG PET/CT:

- 1. SUV_{lesion} (SUV=standardized uptake value)
- 2. SUV_{normal}
- 3. $SUV_{ratio} = SUV_{lesion}/SUV_{normal}$
- 4. PET texture factors: contrast, homogeneity, entropy, skewness, kurtosis
- 5. PET topological factors: eccentricity, solidity, and extent

(SUV=standardized uptake value)

MRI Perfusion:

- 1. V_P (plasma volume)
- 2. K^{trans} (volume transfer coefficient between plasma and extravascular extracellular space)

RSI Diffusion:

1. RSI Celluarity

Either PET/CT or MRI perfusion may be performed first, but both studies should be completed within 12 weeks of each other. The PET/CT will be interpreted by a study nuclear medicine radiologist while blinded to the MRI perfusion results. The MRI perfusion will be interpreted by a study neuroradiologist while blinded to the PET/CT results. Each MRI perfusion metric and each FDG PET/CT metric will be independently tested to predict the diagnosis of radiation injury vs. tumor progression. In addition to independently testing the utility of MRI perfusion and PET/CT in determining radiation injury, we will also examine if combining both techniques will perform better than either one alone.

The protocol proposes using the current standard of practice for diagnosing radiation injury vs. worsening tumor, in terms of histopathology (when available) or clinical and radiological follow up. We will also perform a subcohort analysis to determine if there is any difference between patients diagnosed by histopathology (anticipated at approximately 15-25%) vs. patients diagnosed by follow up.

Clinical and radiological follow up constitute the current standard of practice when histopathology is not available, either due to lesion location (e.g., deep in brain, in brainstem, or in eloquent motor or language areas) or due to patient comorbidities. The table below summarizes several recent papers from the Radiology and Neuro-oncology literature examining the issue of radiation injury. Of the seven cited papers, only one included only pathology proven patients. The other six papers used follow up for diagnosis in 26.7-92.6% of all patients. Our previous paper³⁶ was near the middle of this range, with follow up implemented in 69.9% and using a 6 month minimum follow up time. Although there is no clearly defined clinical and radiological criteria to determine radiation injury, the 6 month minimum follow up approach is more conservative than the 3 months minimum follow up time used by other authors.^{20, 47, 48}

Table. Representative imaging papers studying radiation injury.

Study	# Patients (# lesions)	Tumor type	Technique	# Diagnosis by follow up (minimum follow up)	# Diagnosis by histo- pathology
Barajas et al ²⁰	27 (30)	Metastases	MR perfusion	8 (3 months)	22
Mitsuya et al ⁴⁷	27 (28)	Metastases	MR perfusion	25 (3 months)	2
Narang et al ⁴⁸	29 (29)	Gliomas (n=24), metastases (n=5)	MR perfusion	9 (3 months)	20
Amin et al ⁴⁹	24 (24)	High grade gliomas	DMSA SPECT, MR spectroscopy	19 (not described)	5
Mullins et al ⁵⁰	27 (>39)	High grade gliomas	Conventional MRI	0 (N/A)	27
Langleben et al⁵¹	72 (not described)	High grade gliomas	PET/CT	61 (not described)	11
Young et al ³⁶	93 (not described)	High grade gliomas	Conventional MRI	65 (6 months)	28

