The methods of analysis will include: region-of-interest (ROI) measurements of the lesion and normal brain will be performed. ROIs will be placed in the lesion while avoiding areas of hemorrhage, calcification, and cystic/necrotic change. This is the standard way of measuring lesions in clinical practice. Multiple small ROIs will be placed, and the maximum recorded, a technique that has been described as providing the best reproducibility.^{37, 38} Recorded metrics will include: plasma volume (Vp) and volume transfer coefficient between plasma and extravascular extracellular space (K^{trans}). We may also use volume of interest (VOI) measurements of the entire lesion.

Additional postprocessing: Feature-based analyses will be performed on an investigational basis. These are not routinely performed as part of the standard of care, and therefore the results will be only for research and not included in the MRI report. The DCE maps will be processed using in-house routines developed in C++ and Matlab for extracting image-based textures and Gabor edge features to characterize each lesion in terms of topological and textural factors. In-house developed machine learning techniques may be applied to automatically find correlations between image features and lesion outcomes.

4.2.2. PET/CT: Patients will fast except for water ± medications (as per their clinical physician) for at least 6 hrs prior to this study. The patient is seated comfortably in the injection room and venous access is established. The patency of the venous access is checked with normal saline prior to the administration of the FDG.

Blood glucose is checked by finger stick. If blood glucose is >60 and <200mg/dL the study continues as planned. If the blood sugar is between 200 and 300mg/dL, then a standard insulin administration protocol is used to bring the blood glucose below 200. If blood glucose is > 300mg/dL, the study is rescheduled. If the blood glucose is <60, juice is given orally and the study is rescheduled.

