10 mCi of Fluorine-18 fluorodeoxyglucose (FDG) is injected IV. The patient remains seated quietly in the injection room for 60 minutes. The patient is then positioned on a GE Discovery STE PET/CT. A scout view of the head is acquired at 30 mA, 120 kVp. Once the scanning field is determined from the scout, a spiral CT is acquired using a full helical acquisition at 1 sec/rotation, 30 mA, 140 kV, 5.0 mm slice thickness, 4.5 mm interval. Immediately upon completion of the CT, acquisition of a 10-minute 3D brain PET scan is performed. CT and PET data are re-reconstructed using a 30 cm FOV. CT, PET, and hybrid images are evaluated in transaxial, coronal, and sagittal planes. The standardized uptake value (SUV) of the lesion (SUV_{lesion}), normal brain (SUV_{normal}) and SUV_{ratio} (SUV_{lesion}/SUV_{normal}) will be calculated using standard ROI tools. PET/CT allows whole brain coverage. Measurements of each lesion will be performed and each lesion evaluated independently for radiation injury vs. tumor progression.

Additional postprocessing: Feature-based analyses will be performed on an investigational basis. These are not routinely performed as part of the standard of care, and therefore the results will be only for research and not included in the PET report (as compared to SUV, which are standard of care and reported to the clinician). The PET scans will be processed using CERR (Computational Environment for Radiotherapy Research) and/or in-house routines developed in C++ and Matlab for extracting image-based textures and Gabor edge features to characterize each lesion in terms of topological and textural factors. In-house developed machine learning techniques may be applied to automatically find correlations between image features and lesion outcomes. We may also investigate novel analysis methods in addition to SUV by using other correction factors for normal tissue selection and ratio calculations.

4.2.3 Advanced diffusion imaging (Optional): RSI acquisition will require approximately 4-5 min, similar to the time required for the standard of care DTI acquisition. The only thing noticeable by the patient will be the extra scan time required to acquire DSI. The patient will be requested to remain motionless during this scan.

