To further consider the variation among radiation doses, fractionations and schedules (which may be employed as per the standard of care for the specific tumor type in each patient), a more complicated ANCOVA (analysis of variance with covariates) will be used with the above parameters specified as covariates. If the numbers are small, we will summarize the results descriptively and suggest future research directions. We estimate that 15-25% (21-35 patients of the total) will undergo repeat surgical resection or biopsy to determine the diagnosis. A separate subset analysis will examine for potential differences between lesions diagnosed by pathology vs. lesions diagnosed by clinical and radiological follow up.

Most of the time, the two imaging methods (i.e., MRI perfusion and PET/CT) are expected to yield concordant results (>80%). Therefore, it is meaningful to compare the predictive power of various MRI perfusion measurements and PET/CT measurements. Due to the multiple comparisons needed, an FDR approach will be employed to control for the family-wise error rate. We may further construct a decision rule by combining results from both techniques in the hope of identifying an even more powerful predictive tool, although its feasibility would depend on the exact number of discordant cases and the individual

predictive power (if both MRI perfusion and PET/CT have sufficient predictive power and there are too few discordant cases then the combination may not show significant improvement).

As mentioned above, an interim analysis will be performed after 1 year or accrual of 48 (1/2 of expected total) subjects. Statistical tools may be adjusted at that time point if necessary to account for higher or lower than expected accruals within subgroups. For example, if many more than expected patients have uncertain outcomes or death before diagnosis (without autopsy), then we will may increase the target accrual to compensate.

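### No internal validation is specified for a fitted combined or machine-learned rule, so scoring it on the lesions that built it would bias its apparent gain over a single test upward

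*Combined protocol and SAP*

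**What the plan says.** Section 7.1 lists the imaging metrics, says each will be tested on its own, and adds that "we will also examine if combining both techniques will perform better than either one alone". That part is a commitment.

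Section 11.1 is more tentative: "We may further construct a decision rule by combining results from both techniques in the hope of identifying an even more powerful predictive tool". It ties feasibility to the number of discordant cases and warns that if "there are too few discordant cases then the combination may not show significant improvement". It gives no form for the rule, no variable list and no way of scoring it.

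Sections 4.2.1 (MRI perfusion) and 4.2.2 (PET/CT) each add texture and edge features and state: "In-house developed machine learning techniques may be applied to automatically find correlations between image features and lesion outcomes". Both label this work exploratory: "Feature-based analyses will be performed on an investigational basis".

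Section 4.1 recruits one cohort, with no lesions reserved for validation. The performance methods in section 11.1 are ROC curves and AUCs, bootstrap confidence intervals for the AUCs and their difference, and q-values for the many metrics. No section mentions a training/test split, cross-validation, optimism correction or external validation.

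**The concern.** A rule fitted to a set of lesions adapts to chance patterns in that set. Scored on the same lesions, its AUC is inflated, and the inflation grows with the number of features relative to the size of the smaller outcome class. A single metric read off directly has no such advantage, so comparing the two AUCs is uneven.

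The tools in section 11.1 do not remove this. A bootstrap interval around an apparent AUC describes its sampling spread, not its optimism. The q-values adjust p-values across separate metrics, not the fitting of a joint rule.

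Section 2.0 asks whether the two scans are complementary and both necessary. An inflated combined AUC could be taken as evidence that both are needed. Section 11.1 also expects the two methods to agree in more than 80% of cases. With 90 + 42 = 132 evaluable lesions, fewer than 0.20 × 132 = 26.4 would be discordant. Any real gain rests on those few lesions, so optimism could easily be mistaken for it.

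**Working it through.** The plan gives no figure for the combined rule or the machine-learned models, so there is none to reproduce. The check asks what happens at the plan's own numbers if a fitted rule is scored on the lesions that built it.

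**Inputs from the documents**
- Metrics (section 7.1): 3 SUV + 5 texture ("PET texture factors: contrast, homogeneity, entropy, skewness, kurtosis") + 3 topological + 2 MRI perfusion = 13.
- Outcomes (section 11.1): about 90 progression and 42 radiation injury. With 8 uncertain these sum to 140, not 150; the split is used as given.

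**Assumptions not in the documents**
- One informative metric with true AUC *A* of 0.7, 0.8 or 0.9, normally distributed, with group separation *d* = √2·Φ⁻¹(*A*) = 0.742, 1.190 or 1.812.
- All other metrics are independent noise, so the combination truly gains nothing.
- Logistic combination; one lesion per patient.

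**Quantities**
- Bias = apparent AUC − AUC of the same fitted rule on new lesions.
- Looks better = apparent AUC exceeds that of the best single metric.
- Falsely significant = paired DeLong test of combination against best single metric, two-sided 5%.

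| *A* | Metrics | Apparent | Best single | New lesions | Bias | Looks better | Falsely significant |
|---|---|---|---|---|---|---|---|
| 0.7 | 2 | 0.707 | 0.701 | 0.694 | 0.013 | 73% | 0.1% |
| 0.8 | 2 | 0.807 | 0.803 | 0.796 | 0.011 | 73% | 0.1% |
| 0.9 | 2 | 0.903 | 0.900 | 0.898 | 0.005 | 71% | 0% |
| 0.7 | 13 | 0.771 | 0.701 | 0.643 | 0.128 | 100% | 39% (40% against the informative metric) |
| 0.8 | 13 | 0.846 | 0.800 | 0.757 | 0.089 | 100% | 32% |
| 0.9 | 13 | 0.928 | 0.899 | 0.869 | 0.059 | 100% | 28% |

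Replicates were 1,000 per two-metric row and 400, 400 and 150 for the 13-metric rows. The standard error of the 28% is √(0.28 × 0.72 / 150) = 0.037.

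**Variations**
- Two metrics correlated at 0.7 (*A* = 0.8): looks better in 73%, falsely significant in 0%.
- Best of the 11 × 2 = 22 PET–MRI pairs (*A* = 0.8): looks better in 94%, by 0.006 on average; significant in 0 of 100.
- All 13 metrics noise: mean apparent AUC 0.69, best single 0.61, true value 0.50.
- 21 features. The documents do not count the DCE-map features, so the extra 8 are purely an assumption: falsely significant in 72% to 83% for *A* of 0.8 and 0.7.

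**Scoring on lesions not used for fitting** (*A* = 0.8, 13 metrics, 200 replicates): apparent AUC 0.844, new lesions 0.756, 10-fold cross-validation 0.741, single metric 0.798. The chance of looking better falls from 100% to 3%, and false significance from about 35% to 0%. For two metrics the chance of looking better falls from about 73% to about 8%.

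**The case against.** A reader might infer that the plan makes a favourable verdict on the combination close to certain whatever form it takes. The documents do not support that, for four reasons, each of which stands.

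- **The form is open.** Section 4.1 has each reader give a binary prediction, and section 11.1 speaks of concordant and discordant cases. Calling a lesion positive when both reads, or either read, is positive involves no fitting, hence no fitting optimism, and can do worse than one read alone. A fitted rule from one PET and one MRI metric is nearly harmless: the apparent gain averages 0.003 to 0.007 and is almost never significant.
- **Same-lesion scoring is not stated.** It is inferred from the single cohort and the silence on validation. The ROC and bootstrap text in section 11.1 is written for the PET and MRI measurements, and no scoring method is given for the combination.
- **The feature work is optional and investigational.** Machine learning is described within each modality, and no section says those features enter the combined rule.
- **The plan is cautious.** It says the combination may show no significant improvement. If significance is the yardstick, the false-positive rate at 13 metrics is about 28% to 40%: well above 5%, but far from certain.

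What the objection does not remove is that nothing in the plan limits how many features enter a rule, and nothing says how a fitted rule is to be scored. The caveat on discordant cases concerns lack of information, not overfitting.

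**Conclusion.** The point holds as a gap in specification. The plan commits to the combination question and permits fitted multi-feature rules in one cohort, but names no internal validation or optimism correction. Should such a rule be scored on its own lesions, the AUC would be biased upward by about 0.06 to 0.13 at 13 metrics. The rule would look better than the best single metric in about 100% of trials where nothing is gained, while on new lesions it would do worse by about 0.03 (0.899 − 0.869) to 0.06 (0.701 − 0.643).

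These sizes rest on a logistic rule, normal and independent noise metrics, one informative metric with true AUC 0.7 to 0.9, and one lesion per patient. Related metrics, such as the SUV ratio and its two components, would change them. A more flexible learner would be expected to overfit more; that was not simulated.

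It would go too far to say that the plan sets out an in-sample comparison, or that every combination is bound to win. The bias is under about 0.015 for one PET plus one MRI metric and absent for a fixed rule on the two reads.

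**What to change.** In section 11.1, state that:

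1. Any fitted combined rule or machine-learned model is assessed by repeated cross-validation or bootstrap optimism correction.
2. Resampling is by patient, so that lesions from one patient stay together, in line with the clustering recognised in section 11.3.
3. Feature selection and tuning are repeated inside each resample.
4. The rule is compared with the single tests only on its corrected AUC.

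A fixed rule on the two binary reads can be exempted if it is written down in advance.

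The cost is SAP wording and computing time, with no extra patients or scans. The reported combined AUC will be lower. Cross-validation can also err slightly low: in the check above it gave 0.741 against 0.756 on new lesions, a shortfall of 0.015.

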7.2 Histopathologic Diagnosis

The diagnosis of radiation injury versus tumor progression will be made using histopathologic findings if resection is determined to be clinically necessary by the treating physician. If pathology indicates a mixed population of tumor cells and treatment effects, then the predominant cell population will be used to determine the patient outcome. If the diagnosis remains unclear based on pathology, then the lesion will be placed in a third category of uncertain, and excluded from statistical analysis. Based on the retrospective results presented in Section 3.2, we anticipate 15-25% (n=13-21) of the patients will undergo surgical resection or biopsy of their increasing lesions.

Based on clinical experience, we anticipate that <10% of these 13-21 patients will have indeterminate pathology results. Resection of the indeterminate lesion in itself may have therapeutic value for both radiation injury and tumor progression. Therefore, we not anticipate that we will be able to use clinical and radiological follow up for these patients with uncertain diagnosis after indeterminate pathology.

7.3 Clinical and Radiological Diagnosis

If tissue sampling is clinically not warranted, then the lesion outcome will be determined after clinical and imaging follow up by the neuro-oncologist and/or radiation oncologist, while blinded to the MRI perfusion and PET/CT results. The accuracy of these nonpathologic diagnoses is expected to be maximized by the follow up process, in which determinations may be made up to 6 months (or more) after presentation of the lesion(s). In many cases, following lesions to determine their natural history is expected to provide the best characterization of the underlying biology. These assessments to determine lesion(s) outcome will be performed approximately every 2 months during the study. Blinding will be performed by a third party (e.g., research study assistant). The results of both MRI perfusion and PET/CT are available in the electronic medical record as individual Radiology reports, and may be mentioned in the clinical notes of the treating physician. The chart records and official radiology reports will be saved and/or printed with redaction of these results, by deleting and/or blacking-out the relevant sentences. The blinding party will also pull up the patient's scans on a computer workstation without the MRI perfusion images and without the PET/CT images. Only the regular MRI images would be reviewed to examine changes in size of the lesion(s).

We will adopt the updated response criteria proposed by the Response Assessment in Neuro-Oncology Working Group⁵² shown in the table, with some modifications as below.

Table 4. Summary of the Proposed RANO Response Criteria

Criterion	CR	PR	SD	PD
T1 gadolinium enhancing disease	None	≥ 50% ↓	< 50% ↓ but < 25% ↑	≥ 25% ↑*
T2/FLAIR	Stable or ↓	Stable or ↓	Stable or ↓	1.
New lesion	None	None	None	Present*
Corticosteroids	None	Stable or ↓	Stable or ↓	NAt
Clinical status	Stable or ↑	Stable or ↑	Stable or ↑	1.
Requirement for response	All	All	All	Any*

Abbreviations: RANO, Response Assessment in Neuro-Oncology; CR, complete response; PR, partial response; SD, stable disease; PD, progressive disease; FLAIR, fluid-attenuated inversion recovery; NA, not applicable.

Specifically, to be classified as radiation injury, the lesion must spontaneously stabilize (stable disease) or decrease (partial response or complete response) on subsequent scans over a minimum of 6 months without new chemotherapy. Lesions that continue to increase (fulfilling criteria for progressive disease) will be considered tumor. If the lesion is stable for <6 months and therefore does not meet above criteria for radiation injury, it will be placed in a third category of uncertain and may be excluded from statistical analysis, unless additional follow up beyond the 6 months shows stability (radiation injury) or enlargement (worsening tumor). Therefore, the designation of uncertain may be only temporary, as we will continue to follow the lesion and the patient whenever possible. If a lesion has an uncertain diagnosis despite continued follow up at the end of the study, it will also be placed in the uncertain category and may be excluded from statistical analysis.

Patients with metastatic disease who have enhancing lesions and receive chemotherapy for systemic disease may be determined to have radiation necrosis if: 1) the systemic chemotherapy does not change during the 6 month follow up period to establish radiation necrosis; and 2) the systemic chemotherapy has no known efficacy for CNS disease. If the lesion diagnosis is uncertain after follow up for reason, including interval changes in systemic chemotherapy or additional radiation therapy for new lesions (unrelated to the initially treated lesion that is being followed) as per their treating physician and the

^{*}Progression occurs when this criterion is present.

florease in corticosteroids alone will not be taken into account in determining progression in the absence of persistent clinical deterioration.

standard of care, then the treated lesion will be placed in the third category of uncertain and excluded from statistical analysis.

